## 15.5 Reporting

Demographic information such as age and race will be tabulated. Descriptive statistics, including means, medians, standard deviations, and ranges for continuous parameters, as well as percents and frequencies for categorical parameters, will be presented. Investigation for outliers and assumptions for statistical analysis, e.g., normality and homoscedasticity will be made. Adverse medical events will be tabulated. NCI toxicity Grade 3 and Grade 4 laboratory abnormalities will be listed.

All patients who receive any study drugs will be included in the toxicity evaluation. All patients who receive study drugs for at least 4 weeks will be included in the efficacy evaluation (modified intention to treat). Deaths, early progression, and other reasons for drop-out of the study prior to 4 weeks will be reported.

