## 6.9 Criteria for Removal from Study

Patients will be removed from study when any of the criteria listed below apply. All patients who initiate protocol treatment will be included in the overall evaluation of response (intent-to-treat analysis). All reasons for discontinuation of therapy should be documented clearly in the medical record.

If a subject discontinues or withdraws from the study, every attempt will be made to get a tissue/tumor biopsy at the end of treatment, along with blood if the subject is able and willing to do so.

Patients may be withdrawn from the study if they experience any of the following:

- Disease progression, per investigator assessment
- Intolerable toxicity to taselisib or enzalutamide. Patients experiencing toxicity to taselisib or enzalutamide can continue on study with single agent enzalutamide or taselisib, respectively, at the discretion of the treating physician. Patients will be followed for disease progression and should continue radiologic assessments every 2 cycles as per the study.

Other reasons for patient discontinuation may include, but are not limited to, the following:

- Non-compliance with the study protocol, including, but not limited to not attending the majority of scheduled visits. The Protocol Chair will determine when non-compliance should lead to removal from study. Note: The patients will still be included in the overall evaluation of response (intent-to-treat analysis).
- Patient personal decision. The reason for discontinuation from the study must be documented. The patients will be included in the overall evaluation of response (intent-to-treat analysis) if any protocol therapy was administered prior to withdrawal.
- If the patient becomes pregnant
- Patient is lost to follow-up
- Study is terminated for any reason

The investigator has the right to discontinue a patient from the study for any medical condition that the investigator determines may jeopardize the patient’s safety if he or she continues in the study; for reasons of noncompliance (e.g., missed doses, visits); or if the investigator determines it is in the best interest of the patient. The Protocol Chair should be notified in such cases.

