#### 10.1.2 Evaluable for objective response:

Only those patients who have evaluable disease present at baseline, have received at least one cycle of therapy, and have had their disease re-evaluated will be considered evaluable for response. These patients will have their response classified according to the definitions stated below. (Note: Patients who exhibit objective disease progression prior to the end of cycle 1 will also be considered evaluable.)

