### 10.3.4 Evaluation of Best Overall Response

The best overall response is the best response recorded from the start of the study treatment until the end of treatment taking into account any requirement for confirmation. The patient’s best overall response assignment will depend on the findings of both target and non-target disease and will also take into consideration the appearance of new lesions.

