## 15.7 Reporting and Exclusions

All patients included in the study must be assessed for safety, tolerability, and response to treatment, even if there are major protocol treatment deviations or if they are ineligible. Each patient will be assigned one of the following categories: 1) complete response, 2) partial response, 3) stable disease, 4) progressive disease, 5) early death from malignant disease, 6) early death from toxicity, 7) early death because of other cause, or 9) unknown (not assessable, insufficient data).

All of the patients who met the eligibility criteria and received study drugs for 4 weeks should be included in the main analysis of the clinical benefit rate. Patients in response categories 4-9 should be considered to have a treatment failure (disease progression). Thus, an incorrect treatment schedule or drug administration does not result in exclusion from the analysis of the response and clinical benefit rate.

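### The main CBR analysis drops patients with under 4 weeks of study drugs, section 6.9 keeps everyone treated, and neither set is tied to the 17 and 37 of the two-stage rule

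*Combined protocol and SAP*

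**What the plan says.** Four places describe who counts towards response.

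- **Section 15.5:** "All patients who receive study drugs for at least 4 weeks will be included in the efficacy evaluation (modified intention to treat". Deaths, early progressions and other drop-outs before 4 weeks are to be reported separately.
- **Section 15.7:** "All of the patients who met the eligibility criteria and received study drugs for 4 weeks should be included in the main analysis" of CBR. It opens by requiring a response assessment for every patient in the study, ineligible ones included. It also says "Patients in response categories 4-9 should be considered to have a treatment failure (disease progression"; those categories cover progression, the early deaths and unknown outcomes.
- **Section 6.9:** "All patients who initiate protocol treatment will be included in the overall evaluation of response (intent-to-treat analysis". On patients who choose to leave, it adds: "The patients will be included in the overall evaluation of response (intent-to-treat analysis) if any protocol therapy was administered prior to withdrawal".
- **Section 10.1.2:** evaluability for objective response needs one cycle and a re-evaluation, but "Patients who exhibit objective disease progression prior to the end of cycle 1 will also be considered evaluable".

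The decision rule is in section 15.3: a Simon optimal two-stage design, 20% against 40%, continuing with at least 4 successes in 17 and declaring the regimen worthy with at least 11 in 37. The interim is timed for when the first 17 phase II patients have finished two cycles and been scanned. Replacement is mentioned only for phase I. Section 15.4 adds phase Ib patients treated at the recommended dose to the evaluable phase II patients, without defining evaluable.

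**The concern.** A patient who dies or progresses before week 4 can hardly reach CR, PR or stable disease of at least 16 weeks. Under section 6.9 that patient is a failure in the denominator. Under sections 15.5 and 15.7 the patient is absent from it. Two analysts following the protocol could therefore report different values of the primary endpoint from the same data. The choice would also be open after the outcomes are known, because the trial is open-label.

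The decision rule depends on exact counts in 17 and 37 patients. If it is unclear whether those are treated patients, 4-week patients or patients with two cycles and a scan, it is also unclear whether the stated 10% error rates apply.

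The 4-week condition is itself loose, because section 15.5 does not say which drug or drugs it refers to. Sections 6.3.1 and 7.2.1.3 give a 28-day enzalutamide lead-in before taselisib, so 4 weeks can be met on enzalutamide alone. Section 6.9 also says "Patients experiencing toxicity to taselisib or enzalutamide can continue on study with single agent enzalutamide or taselisib, respectively".

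**Working it through.** **1. The plan's own figures.** Inputs from section 15.3: n1 = 17, continue at 4 or more; n = 37, worthy at 11 or more; p0 = 0.20; p1 = 0.40; type I and type II error 10% each; 55% chance of stopping early under the null.

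P(worthy | p) = Σ(x = 4 to 17) Bin(x; 17, p) × P[Bin(20, p) ≥ 11 − x]; P(stop early | p) = P[Bin(17, p) ≤ 3].

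- p = 0.20: P(worthy) = 0.0948; P(stop early) = 0.549.
- p = 0.40: P(worthy) = 0.9033.

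The stated design is reproduced.

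**2. Effect on the reported rate.** Let d be the share of treated patients excluded, q their success rate and pk the success rate of those kept. The all-treated rate is p = (1 − d)pk + dq, so pk − p = d(pk − q). The 4-week rate is too high, relative to the all-treated rate, exactly when q < pk. The documents give no value for d, so the exclusions below are assumptions.

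| Of 37 treated, 11 successes | Reported CBR |
|---|---|
| none excluded | 11/37 = 29.7% |
| 2 failures excluded | 11/35 = 31.4% |
| 4 failures excluded | 11/33 = 33.3% |
| 4 excluded, one of them a success | 10/33 = 30.3% |

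For progression and death before week 4, q is essentially zero. For other early drop-outs it is less settled. Section 10.3.4 says "The best overall response is the best response recorded from the start of the study treatment until the end of treatment", while section 10.4 runs stable disease to progression and section 6.8 follows progression only annually.

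**3. Effect on the go/no-go error.** This depends on what the 17 and 37 count.

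- *37 treated patients, fixed counts of 4 and 11, no replacement.* Removing failures from the denominator leaves the success counts unchanged. P(worthy | 0.20) = 0.0948 for every d.
- *17 and 37 filled with 4-week patients.* A true all-treated rate of 0.20 becomes 0.20/(1 − d) if every excluded patient is a failure, and (0.20 − 0.10d)/(1 − d) if 10% of them would have succeeded.

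| d (assumed) | Rate, all failures | P(stop early) | Type I error | Type I error if 10% succeed |
|---|---|---|---|---|
| 5% | 0.2105 | 0.505 | 0.125 | 0.1095 |
| 10% | 0.2222 | 0.458 | 0.166 | 0.1274 |

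**4. Cost of the all-treated rule if 20% and 40% describe a 4-week set.** The rates become 0.20(1 − d) and 0.40(1 − d), taking all early drop-outs as failures.

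| d (assumed) | Rates | Type I error | Power |
|---|---|---|---|
| 0 | 0.20, 0.40 | 0.095 | 0.903 |
| 5% | 0.19, 0.38 | 0.071 | 0.858 |
| 10% | 0.18, 0.36 | 0.051 | 0.799 |

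**The case against.** The best defence is that the protocol has two tiers. Sections 15.5 and 15.7 agree on 4 weeks, and section 15.7 names that set for the main CBR. Section 6.9 concerns removal from study and speaks of an overall evaluation of response. On this reading everyone is assessed, the main CBR uses the modified set, and early drop-outs are listed so that an all-treated rate can be recomputed. This stands in part: it would be wrong to say that no set is named for the main CBR. But section 6.9 uses the intent-to-treat label without limiting it to a secondary analysis, section 15.7 scores as failures patients whom its own condition removes, and nothing connects either set to section 15.3. The interim wording there adds a third description. One could also say that including 4-week patients does not exclude the rest, but the modified intention-to-treat label and the separate reporting of early drop-outs point to exclusion.

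A second defence is exposure. Under the lead-in, a patient lost before 4 weeks has had no taselisib, so the condition removes patients never exposed to the combination. That is a fair reason to show the 4-week set, though the condition does not ensure exposure: 28 days of enzalutamide can satisfy it.

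Three stronger readings are tempting and are not supported:

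- *The comparison with the 20% null is biased.* That figure comes from a prior bicalutamide study, and the protocol does not give its denominator. If it was a 4-week or evaluable-set rate, the 4-week analysis compares like with like.
- *The type I error exceeds 10%.* It does so under the filled-set reading above. Section 15.3 provides no phase II replacement, and with 37 treated patients and fixed counts the error does not move.
- *The rash experience shows heavy exclusion.* Section 7.2.1.3 reports grade 3 or 4 rash with fever in 7 of 8 combination patients within 14 days, but before the lead-in, and does not say how many stopped treatment. Section 6.9 allows single-agent continuation, and section 15.7 does not exclude patients for incorrect drug administration.

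**Conclusion.** The point holds as a conflict over the primary analysis set that should be fixed. Sections 15.5 and 15.7 take early deaths and progressions out of the main CBR denominator, section 6.9 keeps them in, section 10.1.2 counts cycle 1 progression as evaluable, and section 15.3 is tied to none of these rules.

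Relative to an all-treated CBR, the direction is upward as long as excluded patients succeed less often than those kept, which is close to certain for deaths and progressions before week 4. The size is about 2 to 4 percentage points for 2 to 4 excluded failures (31.4 − 29.7 = 1.7; 33.3 − 29.7 = 3.6), but the number excluded is an assumption. Whether the comparison with 20% is also biased cannot be settled from the documents. Inflation of the go/no-go error is conditional on filling the 17 and 37 with 4-week patients.

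**What to change.** 1. In sections 15.3, 15.5 and 15.7, define the primary CBR set, and the 17 and 37, as all combination-arm patients who receive any study drug (the section 6.9 rule), together with the phase Ib patients already included by section 15.4, without replacement.
2. Count as a failure any progression, death or loss before the 16-week assessment without a prior CR or PR. Allow for the study calendar's scan window: 16 weeks is 112 days, so a compliant second scan can fall at 112 − 5 = 107 days.
3. Align section 10.1.2 and the interim wording in section 15.3 with this set.
4. Report the eligible, at-least-4-week set as a labelled sensitivity analysis. State which drug or drugs the 4 weeks refer to, because patients lost during the enzalutamide lead-in receive no taselisib.
5. State that the 20% and 40% refer to the primary set.

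The cost is wording in these sections and a slightly lower reported CBR. If the 20% and 40% refer to all treated patients, the stated error rates are kept. If they were meant for a 4-week set, power falls from 0.903 to 0.858 or 0.799 at 5% or 10% early drop-out, and the sponsor should accept that openly or revisit the sample size.

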## 15.6 Analysis of Secondary Endpoints

We will calculate the ORR and corresponding 95% confidence intervals at the dose recommended for phase II. The overall PFS data for the patients at the dose recommended for phase II will be estimated using the Kaplan-Meier method with 95% confidence intervals.

Biopsy analysis will be performed in conjunction with the Pathology and Tissue Informatics Core to assess baseline, therapy-induced changes and status upon progression of the following: proliferation (Ki67), mitosis (mitotic index), apoptosis (cleaved caspase 3 levels by IHC), genomic instability (H2AX by IHC), levels of PTEN by IHC, PI3KCA mutational analysis, HER2 (IHC, FISH) and ER/PR levels (IHC). Levels of MEK [total and phosphorylated ERK1/2 (pERK1/2)] and AKT [phosphorylated AKT, S473 (pAKT)] will be measured by IHC.

RNA-seq will be performed on all biopsies to assign a triple negative subtype, to determine baseline and treatment-induced changes in GE after 5-10 days of therapy and define mutations present in the tumors both at baseline and upon progression of the disease. We expect an enrichment of drug resistance-associated mutations/gene amplifications particularly in tumors that regress and later recur while on therapy. Somatic SNPs and structural variants will be validated by whole exome sequencing (WES) of genomic DNA from the tumor and matched blood. We will validate mutations by targeted capture approaches that allow high-level coverage (greater than 200X) and analysis of clonality. The status of p53, BRCA1/2, PIK3CA, PTEN, INPP4B and other mutations associated with TNBC in the tumor tissue is critical for testing our hypothesis. This genetic information is key for determining the prognostic significance of mutations relative to response of agents being tested and for understanding mutation selection relative to the underlying genetic milieu of each tumor at time of entry into the trial. We anticipate significant opportunity for discovery of novel mutations as well as those arising from selection during resistance to the therapies under investigation. Statistics on the correlative endpoints (tissue assays and MRI scan) will be primarily descriptive. Therefore, these studies are considered to be exploratory and potentially hypothesis-generating.

Pharmacokinetic samples are being collected in all patients to assess concentrations of GDC-0032 and enzalutamide and estimate PK parameters, as appropriate. Plasma samples may be used for exploratory analysis to evaluate potential taselisib-related metabolites and/or exploratory biomarker development.

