- l Tumor assessment should be performed approximately every 2 cycles (up to -5 days) while on study treatment and at End-of-treatment visit if not obtained within the past 6 weeks. Scans should consist of CT scan of the chest, abdomen, and pelvis and a bone scan at baseline. Subsequent scans should consist of CT chest, abdomen and pelvis, and bone scan if bone metastases were present on the baseline studies. At the end of treatment, all scans (baseline and through disease progression) should be sent on a CD to the Vanderbilt Cancer Imaging Support Laboratory for central review and assessment. See Section 10.5 for details and address.
- m Archived tumor biopsy specimen: 20 unstained slides of archived biopsy block (unstained slides) or fresh tumor biopsy will be requested at the time of enrollment prior to initiation of treatment.
- n Tumor biopsies will only be performed in the phase II portion. A tumor biopsy from a metastatic site will be obtained from patients prior to day 1, at cycle 2 day 14-21, and upon progression of disease. The third biopsy (at the end of treatment) will not be required for patients who are removed from study for reasons other than disease progression. A patient who undergoes a research biopsy procedure for the purpose of this protocol, and in whom inadequate tissue is obtained, is not obligated to undergo a repeat biopsy.
- o See section 9.1. Required only for patients at Vanderbilt and only in the phase II portion. This should be performed prior to tumor biopsy, if possible. If MRI sub-study is not feasible due to scheduling, MRI weight limits, etc., patients may still continue with the remainder of the study.
- p Subjects on the enzalutamide + taselisib arm should begin enzalutamide on day 1 of cycle 1, and taselisib on day 1 of cycle 2.
- q Pill Diary can be found in the packet of supplemental forms.
- r See Section 6.4.2.
- s Phase II only. Biopsy questionnaire should be filled out by the patient on C3D1. Form can be found in the packet of supplemental forms.
- t The cycle 2 day 8 visit is only needed for patients on the combination of taselisib + enzalutamide. Patients on enzalutamide only do not need a visit on this day.

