## 1. STUDY DESIGN/SUMMARY

This is an open-label phase Ib/II multiple institution trial that evaluates the safety profile and efficacy of enzalutamide with or without taselisib in patients with androgen receptor positive triple negative metastatic breast cancer (AR+ TN MBC). The phase 1b portion will allow any ER/PR status, provided the patient is HER2 negative. Patients with AR positivity, defined as  $\geq 10\%$  of tumor cell nuclei with immunoreactivity for AR, will receive enzalutamide +/- taselisib. All patients in the phase Ib portion will receive both drugs. Patients in the phase II portion will undergo core biopsy of a metastatic lesion (if reasonably safe) at baseline, at day 14-21, and at the time of progression. If a fresh biopsy is deemed not safe, a paraffin block from a prior biopsy or surgery must be available for enrollment. Standard staging radiology scans will be performed at baseline and every 2 cycles (up to - 5 days) thereafter. Upon progression of disease by RECIST, patients on the enzalutamide only arm will be allowed to crossover to enzalutamide + taselisib. Those on the combination arm will be removed from study. Patients will be screened and enrolled from the oncology practice at the Vanderbilt-Ingram Cancer Center, from participating member centers of the Translational Breast Cancer Research Consortium, and from other approved sites.

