### 6.3.1 Taselisib

Taselisib tablets are administered once daily until disease progression or intolerable toxicity. Taselisib administration will begin on C2D1 for patients enrolled on the combination arm (with enzalutamide alone beginning on C1D1). Each dose should be taken with a minimum of 3–4 ounces (90–120 mL) of water with or without food in the morning (before noon). If a dose is missed (not taken by noon), the patient will resume dosing with the next scheduled dose. Missed or vomited doses will not be made up. The occurrence and frequency of any vomiting during a treatment cycle must be noted as an adverse event. Patients should swallow the capsules as a whole and not chew or crush them.

A sufficient number of taselisib tablets should be provided to the patient to last until the next cycle. Patients will be instructed to bring their bottles of study drug and their medication diary with them to each study visit.

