## **9. CORRELATIVE/SPEIAL STUDIES**

## 9.1 Advanced imaging correlative (Vanderbilt only)

Patients enrolling at Vanderbilt will be screened for participation in an advanced imaging correlative study, to be conducted through collaboration with investigators at the Vanderbilt University Institute for Imaging Science (VUIIS). The advanced imaging correlative will consist of multiparametric magnetic resonance imaging (MRI) to be performed at the VUIIS facility at three timepoints, chosen to coincide with the timing of required core biopsies: baseline, at day 14-21 following treatment initiation, and at the end of treatment.

Multiparametric MRI examinations will be designed and made available for four body sites – breast/axilla, lower neck/supraclavicular region, liver, and pelvic bone marrow – and patients will be eligible to participate in the advanced imaging correlative if their required core biopsies are obtained from one of these four body sites. Participation will be mandatory for patients accruing at Vanderbilt who meet the criteria outlined below, including presence of measurable disease (defined as at least one lesion measuring at least 10 mm in long axis diameter) at the body site of interest. If participation in the MRI sub-study is not possible due to scheduling issues, MRI weight limits, eligibility, or safety concerns over implanted medical devices, subjects may still continue with the rest of the study.

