### 9.1.1 Background and rationale

Oncologic imaging is in the midst of a paradigm shift in which a number of advanced quantitative techniques reporting on tissue function and composition at the molecular level are now being advanced as candidate biomarkers for cancer detection, characterization, and treatment response assessment. This advanced imaging correlative deploys several promising MRI techniques within a single multiparametric MRI examination. The overall hypothesis for the advanced imaging correlative is that these techniques, either individually or in combination, can provide clinically useful information beyond that provided by standard-of-care imaging in the context of metastatic TNBC. The components of the multiparametric MRI examination, and hypotheses related to these components, are outlined briefly below:

- **Dynamic contrast enhancement MRI (DCE-MRI)** is a method for characterizing tissue vascularity. The technique involves rapid acquisition of serial MR images before, during, and after injection of an intravenous contrast agent; these images are then analyzed with mathematical models to estimate quantitative values for pharmacokinetic and tissue properties. We hypothesize that early changes in these derived DCE-MRI parameters (i.e., from baseline to day 14-21) will predict treatment response. We will also test whether baseline DCE-MRI parameters by themselves predict patient response to treatment, whether baseline DCE-MRI parameters can discriminate between AR+ and AR- subtypes of TNBC, and whether DCE-MRI parameters at the time of progression are significantly different from DCE-MRI parameters at baseline and early during therapy. Finally, we will evaluate the correlation between DCE-MRI parameters and phosphorylated p-ERK1/2, p-S6, and p-AKT S-473 levels at serial core biopsies.
- **Diffusion-weighted MRI (DW-MRI)** is a method for quantifying tissue cellularity. The technique reports on the ability of water molecules to move randomly, or diffuse, within tissue; more cellular tissues tend to have more barriers to water movement and, therefore,

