### 9.1.3 MRI Imaging procedures

Patients will undergo multiparametric MRI at baseline, at day 14-21, and at the end of treatment. The multiparametric MRI examinations should be scheduled to coincide with the planned core biopsies as much as is reasonably practical. At any given timepoint, however, **every effort should be made to complete the MRI examination before the core biopsy**, because hemorrhage from the core biopsy may interfere with the MRI measurements.

The general scan order and anticipated scan durations are summarized below:

1. Scout images, transmitter tuning, shimming, slice prescription – 5 min
2.  $T_1$  map – 2.5 min
3. Diffusion-weighted MRI (DW-MRI) – 5 min
4. Chemical exchange saturation transfer (CEST-MRI) – 10 min
5. Pre-contrast  $T_1$ -weighted anatomic MRI – 2 min
6. Dynamic contrast-enhanced MRI (DCE-MRI) – 8 min  
\*Intravenous injection of the FDA-approved contrast agent (CA) Magnevist® (gadopentetate dimeglumine, 0.1 mmol/kg) 60 sec after the start of the scan. Infusion time is 5-10 sec, depending on patient weight. CA will be followed by saline flush.
7. Post-contrast  $T_1$ - and  $T_2$ -weighted anatomic MRI – 10 min

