### 9.2.3 Fresh biopsy of metastatic site

Once a patient is confirmed to be AR positive, meets all other eligibility, and registers for the study, collection of tissue from a metastatic site, if reasonably safe, is also a requirement for entry to this study. A biopsy can also be used for AR testing for the study (see Section 5). Pre-trial and day 14-21 biopsies should be collected. Research tissue blocks prepared from

these metastatic biopsies will not be returned. **All patients must have a biopsy of a metastatic site at the end of treatment if the patient is removed for disease progression or is on the enzalutamide only arm and crossing over to enzalutamide + taselisib. See section 9.2.4 below for details on collecting tissue.**

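### The on-treatment biopsy and MRI time point differs between sections 15.6, 9.1 and the Study Calendar, and the versions imply different taselisib exposure

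*Combined protocol and SAP*

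**What the plan says.** Phase II patients have a biopsy at baseline, one on treatment and one at progression. Vanderbilt patients also have multiparametric MRI, timed to go with the biopsies. The on-treatment time point is written in three ways.

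- **Section 15.6**, on RNA-seq of the biopsies: "to determine baseline and treatment-induced changes in GE after 5-10 days of therapy".
- **Section 9.1**, on MRI: "baseline, at day 14-21 following treatment initiation, and at the end of treatment". Four other places give the same days with no cycle: section 1 ("at baseline, at day 14-21, and at the time of progression"), section 9.1.1 ("early changes in these derived DCE-MRI parameters (i.e., from baseline to day 14-21) will predict treatment response"), section 9.1.3 ("Patients will undergo multiparametric MRI at baseline, at day 14-21, and at the end of treatment") and section 9.2.3 ("Pre-trial and day 14-21 biopsies should be collected").
- **Study Calendar**, footnote n, on biopsies: "prior to day 1, at cycle 2 day 14-21, and upon progression of disease". The calendar grid places the MRI under cycle 2 as well.

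On drug start, section 6.3.1 says: "Taselisib administration will begin on C2D1 for patients enrolled on the combination arm", with enzalutamide alone from C1D1. Calendar footnote p agrees, and section 7.2.1.3 explains the 28-day lead-in as an amendment made after rash in combination patients. Sections 6.2.1 and 9.5 still carry another order for Vanderbilt combination patients: taselisib from day 1 and enzalutamide from day 9. Section 9.5 limits this to the first ten.

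**The concern.** An on-treatment change can be interpreted only if the reader knows which drugs the patient had taken, and for how long. With the lead-in, the cycle in which the sample falls decides whether it shows enzalutamide alone or the combination. A site working from 9.1 would sample in cycle 1 and a site working from the calendar in cycle 2, and both specimens would be filed as the on-treatment sample.

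Two sets of analyses depend on it: the therapy-induced tissue changes in 15.6 (Ki67, apoptosis, pERK, pAKT, gene expression), and the hypotheses in 9.1.1 that early MRI change predicts response and correlates with phosphoprotein levels in the serial biopsies. A cycle 1 sample from a combination patient on the lead-in cannot show a taselisib effect. In both arms the duration of enzalutamide at sampling would also differ by 28 days between the two readings.

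**Working it through.** The plan gives no figure to reproduce here. The check converts each window to study days and looks for overlap.

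**Inputs.** Cycle length is 28 days (phase II schema). The first taselisib dose on the combination arm is on C2D1 (section 6.3.1, footnote p). The windows are those set out above. The general visit allowance is 3 days (calendar footnote a, section 6.5).

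**Formulas.** With C1D1 as day 1, study day = (cycle − 1) × 28 + day. Day of a drug = study day − first-dose study day + 1.

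- First taselisib dose: 28 + 1 = study day 29.
- Calendar window: 28 + 14 = 42 to 28 + 21 = 49. Day of taselisib: 42 − 29 + 1 = 14 to 49 − 29 + 1 = 21.
- Section 9.1 window from C1D1: study days 14-21, ending 29 − 21 = 8 days before the first taselisib dose. Counted as elapsed days (15-22) with the 3-day allowance added, the latest day is 25, still 4 days before it.
- Section 15.6 window: study days 5-10 from C1D1, or 29 + 4 = 33 to 29 + 9 = 38 from taselisib start.

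| Source | Study days | Day of enzalutamide | Day of taselisib |
|---|---|---|---|
| 15.6, from C1D1 | 5-10 | 5-10 | none |
| 15.6, from C2D1 | 33-38 | 33-38 | 5-10 |
| 9.1, from C1D1 | 14-21 | 14-21 | none |
| Calendar | 42-49 | 42-49 | 14-21 |

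Neither reading of 15.6 overlaps 14-21 or 42-49. Contact appears only if elapsed days are counted in 15.6 and the visit allowance is also taken off the biopsy window. Even then it is a single edge day: day 39 from taselisib start against the calendar (42 − 3), or day 11 from C1D1 against the day 14-21 given without a cycle (14 − 3).

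**Start order in 6.2.1 and 9.5.** With taselisib on day 1 and enzalutamide on day 9, study days 14-21 would be day 14-21 of taselisib and day 6-13 of enzalutamide (14 − 9 + 1 = 6; 21 − 9 + 1 = 13). The same MRI window would then fall on both drugs. These sections contradict 6.3.1, 7.2.1.3 and footnote p, and the passages must be reconciled.

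**Patients treated before the lead-in.** Section 7.2.1.3 reports 8 patients on the phase II combination arm before the amendment. If all 8 count toward the maximum of 37 in section 15.3, that is 8/37 = 22% of the arm with a different sequence.

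**The case against.** The strongest reply is that the schedule is clear enough. Section 6.5 sends sites to the Study Calendar, which puts biopsy and MRI in cycle 2. Sections 1, 9.1.1, 9.1.3 and 9.2.3 omit the cycle and do not name a different one. Much of this stands: divergence between sites is a risk, not something the documents show. But section 9.1 does fix its window from the start of treatment, and calendar footnote o refers MRI users to that section.

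A reader could also take treatment initiation in 9.1 to mean the first taselisib dose, which would match the calendar for the combination arm. The text does not say so, and the enzalutamide-only arm has no taselisib start before crossover. C1D1 is the natural reading, but it is a reading.

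Several stronger inferences are tempting and not supported:

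- *That 15.6 has no specimen to analyse.* RNA-seq is planned on all biopsies, so specimen and assay exist; the time label is wrong.
- *That the lead-in caused the 15.6 mismatch.* Five to ten days does not match day 14-21 without the lead-in either.
- *That the p-AKT and p-S6 objectives depend on this sample.* Section 2.3 sets both at baseline and progression. On-treatment use comes from 15.6 (which does not list p-S6) and the MRI correlations in 9.1.1.
- *That only the calendar window falls on taselisib.* Five to ten days from C2D1 also does, as does day 14-21 under the 9.5 start order.
- *That a pooled effect is diluted by some percentage, or that every combination patient is affected.* The documents give no fraction of sites following each section, and plan no pooled mean taselisib effect. MRI is done at one site, so mixing between sites cannot apply to it. Patients without an accessible lesion may enrol on archived tissue, and inadequate biopsies need not be repeated.

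**Conclusion.** The inconsistency is real and sits in operative text. The 9.1 and calendar windows are 28 days apart. For a combination patient on the lead-in they mean no taselisib versus 14-21 days of it, taking treatment initiation as C1D1 and assuming uninterrupted dosing. Section 15.6 names a time at which no biopsy is scheduled. The older start order in 6.2.1 and 9.5 adds a further conflict at the only site doing MRI.

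The reach is limited. Section 15.6 calls the correlative statistics primarily descriptive and exploratory, and no direct comparison of the arms is planned. CBR, PFS, ORR and sample size are unaffected. It still merits correction, because the sample is an invasive research biopsy, required where a lesion is reasonably accessible, and one written rule would place it in a different exposure period from another.

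**What to change.** 1. State one cycle and day range for the on-treatment biopsy and MRI, identically in sections 1, 9.1, 9.1.1, 9.1.3, 9.2.3 and 15.6 and in the calendar, and name the dose from which days are counted.
2. Correct the 5-10 day label in 15.6 so that it describes the biopsy actually collected.
3. Reconcile the Vanderbilt start order in 6.2.1 and 9.5 with the lead-in in 6.3.1, 7.2.1.3 and calendar footnote p.
4. Record, for each on-treatment biopsy and MRI, the actual days since first dose of each drug, and analyse change on that basis.
5. Report separately, rather than exclude, combination-arm samples taken before any taselisib and samples from patients treated before the lead-in amendment. Exclusion could lose up to 8 of at most 37 combination patients, and the wording conflict does not require it.

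The cost is an amendment to the wording, one derived variable and smaller descriptive subgroups. No extra biopsy or scan is needed.
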